6.6 Packaging and Labeling

6.6.1 Investigational Product

Details regarding IP packaging, labeling, and use instructions will be provided in a separate Study Reference Manual (SRM).

6.6.2 Blinding of Treatment Assignment

Not applicable. This is an open-label study.

6.7 Concomitant Medications and Procedures and Other Restrictions

6.7.1 Concomitant Medications and Procedures

No concomitant medications (prescription, OTC, and herbal), with the exception of paracetamol up to 650 mg/day (not to exceed 2000 mg total in the 7 days before the first treatment with DARE-HRT1), no personal lubricants (with the exception of water-based lubricants), or intravaginal products may be administered during the study unless they are prescribed by the investigator for treatment of specific clinical events. No concomitant procedures will be performed during the study unless approved by the investigator. No vaccinations are allowed

CONFIDENTIAL

other than for coronavirus disease 2019 (COVID-19) unless approved by the investigator. All medications (prescription and OTC), vitamin and mineral supplements, and herbal remedies taken during the study will be documented on the concomitant medication electronic case report form (eCRF). Information recorded will include: start and stop dates and times, dose and route of administration, and indication. Medications taken for a procedure will also be included, as well as the procedure itself.

6.7.2 Other Restrictions

Participants will be instructed to adhere to the following restrictions:

- Participants must comply with the CRU smoking policy, if applicable
- Participants are not permitted to participate in any other clinical trial or donate blood or plasma while participating in this clinical trial.

7 STUDY ASSESSMENTS AND PROCEDURES

Participants will undergo study procedures and assessments at time points specified in the schedule of events ([Table 1-1](#)).

7.1 Medical and Surgical History

The investigator or designee will collect a complete medical and surgical history at screening. Medical and surgical history will be collected on Cycle 1 Day 1 to determine if any changes have occurred since screening.

7.2 Demographic Characteristics

Demographic characteristics including sex, age, race, and ethnicity will be recorded.

7.3 Physical Measurements

Height (cm) and body weight (kg) without shoes will be recorded and BMI will be calculated.

7.4 Daily Diary

Participants will use a paper diary to document insertion and removal of the IVR and any instances of the IVR falling out, as well as any concomitant medication use (see [Appendix C](#)). Diaries will be dispensed at screening, and participants should bring the diary to study visits in accordance with the schedule of events ([Table 1-1](#)) for review.

7.5 Training

Participants will be trained how to use the IP in accordance with the schedule of events ([Table 1-1](#)).

7.6 Pharmacokinetic Assessments

7.6.1 Drug Concentration Measurements

Plasma PK samples will be collected at time points specified in the PK sampling schedule within the schedule of events ([Table 1-1](#)). Blood sample collection, processing, and shipping details will be outlined in a separate SRM.

Plasma concentrations of estradiol, estrone, and progesterone will be determined using a validated method.

7.6.2 Pharmacokinetic Parameters

Pharmacokinetic variables will be calculated from the plasma concentration data using noncompartmental methods (Phoenix™ WinNonlin®, Version 6.4 or later; Certara LP, Princeton, New Jersey, USA) and actual sampling times.

The following PK parameters will be determined:

C_{ss} Steady-state concentration

CONFIDENTIAL

C_{\max}	Maximum observed plasma concentration
t_{\max}	The time that C_{\max} was observed
AUC_{D1-D29}	Area under the plasma concentration-time curve from time 0 (Day 1) to the time of the last quantifiable concentration on Day 29; calculated using the linear/log trapezoid rule

Baseline correction, using the average of the 3 predose concentrations on Day 1, may be performed prior to the calculation of PK parameters by noncompartmental methods. The C_{\max} (and t_{\max}) will be computed over each 24-hour PK profile (Day 1 of each cycle) and over the entire 28-day treatment interval. Additional PK parameters may be calculated as appropriate.

7.7 Safety Assessments

7.7.1 Adverse Events

Participants will be monitored for AEs from the time of consent. Treatment-emergent AEs (TEAEs) will be those with an onset after insertion of the first IVR through the follow-up telephone call. Serious adverse events will be collected beginning at ICF signing and in an ongoing manner through the follow-up telephone call. Refer to Section 8 for additional details.

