5.2 Exclusion Criteria

Participants will not be eligible for study participation if they meet any of the exclusion criteria, or will be discontinued at the discretion of the investigator in consultation with the medical monitor if they develop any of the exclusion criteria during the study.

1. Prior abnormal cervical screening test or Papanicolaou result within 2 years of screening. Participant can have atypical squamous cells of undetermined significance, if human papillomavirus negative.
2. Participants with any self-reported active sexually transmitted disease and/or evidence of infection based on vaginal visual examination by the investigator.
3. Participants with a urinary tract infection during screening as assessed by urine dipstick test with abnormal test findings (any positive result for leukocytes AND any positive result for nitrites).
4. Have a history of endometrial hyperplasia or cervical or uterine carcinoma.
5. Participants with indwelling catheters or requiring intermittent catheterization.
6. Participants with multiple or unsuccessful (e.g., still having symptoms) pelvic reconstructive surgery, or who suffer from pelvic relaxation.
7. Participants who have had a hysterectomy.
8. Participants taking any estrogen and/or progesterone products who are not willing to stop this treatment during their participation in this trial (see Section 4.1 for washout requirements). Participants who are using HRT that requires more than 8 weeks to wash out (e.g., progestogen implants or progestogen injectable drug therapy, estrogen alone injectable drug therapy or estrogen pellet therapy) will not be eligible.
9. Participants with concomitant use of personal lubricants (water-based lubricants are allowed) or any intravaginal product or medication, either by prescription or over-the-counter (OTC) (e.g., Femring [estradiol acetate vaginal ring], ESTRING[®] [estradiol vaginal ring]) with the exception of those who agree not to use these products during the IVR use period.
10. Self-reported or observed vaginal irritation unrelated to VVA; vaginal, vulvar, or cervical lesions, undiagnosed vaginal bleeding; or tenderness.
11. Participants with a finding of clinically significant uterine fibroids at screening.

CONFIDENTIAL

12. Participants with a known hypersensitivity to progesterone, estradiol, Femring, or the components of the IVR (e.g., ethylene vinyl acetate).
13. Participants with prior pelvic malignancies.

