7.8.4 Most Bothersome Symptom

At the Cycle 1 Day 1 Visit, participants will rate the first 4 items in the list of VVA symptoms in [Table 7-2](#) as either not present (none), mild, moderate, or severe, and will indicate whether vaginal bleeding associated with vaginal activity is present or absent. They will then select 1 of the 5 symptoms as their most bothersome symptom. All 5 symptoms will be evaluated again during later study visits (see [Table 1-1](#)), and the change in severity from baseline will be determined. Changes from baseline in each participant's most bothersome symptom will be evaluated.

CONFIDENTIAL

Table 7-2: Assessment of Most Bothersome Symptom

Symptom	Assessment
Vaginal dryness	None, mild, moderate, or severe
Vaginal and/or vulvar irritation/itching	None, mild, moderate, or severe
Dysuria	None, mild, moderate, or severe
Vaginal pain associated with sexual activity (dyspareunia)	None, mild, moderate, or severe
Vaginal bleeding associated with sexual activity	Presence versus absence

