8 ADVERSE EVENTS

An AE is defined as any untoward medical occurrence in a participant administered a pharmaceutical product during the course of a clinical investigation. An AE can therefore be any unfavorable and unintended sign, symptom, or disease temporally associated with the use of a study drug/product, whether or not thought to be related to the study drug/product.

Participants will be monitored for AEs throughout the study from the time of consent. Treatment-emergent AEs (TEAEs) will be those with an onset after insertion of the first IVR through the follow-up telephone call. Adverse events that are identified at the last assessment visit (or the early termination visit) as specified in the protocol must be recorded on the AE eCRF with the status of the AE noted. All events that are ongoing at this time will be recorded as ongoing on the eCRF. All (both serious and nonserious) AEs must be followed until they are resolved or stabilized, or until reasonable attempts to determine resolution of the event are exhausted. The investigator should use his/her discretion in ordering additional tests as necessary to monitor the resolution of such events.

The procedures specified in Section 8.4 are to be followed for reporting SAEs.

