9.4 Endpoints

9.4.1 Primary Endpoints

The primary endpoints are as follows:

- Incidence and severity of AEs
- Changes from baseline in clinical laboratory findings
- Changes from baseline in physical examination findings
- Changes from baseline in vital signs results
- Changes from baseline in speculum examination findings
- Changes from baseline in transvaginal ultrasound findings
- Steady-state concentration (C_{ss}) and maximum observed plasma concentration (C_{max}) in each cycle for estradiol, estrone, and progesterone

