9.6 Safety Analysis

Adverse events, concomitant medications, clinical laboratory findings, physical examinations, speculum examination findings, transvaginal ultrasound results (and endometrial biopsy findings if required), and vital signs for each participant will be tabulated or summarized descriptively, where appropriate.

Vital signs data (observed and change from baseline) will be summarized by time point and treatment using appropriate descriptive statistics. Using the safety population, changes from baseline at each post-randomization visit and end of treatment will be compared between treatment arms. Qualitative analysis of laboratory tests in terms of abnormality will be performed. Findings on physical examination at screening and end of treatment will be reported and compared.

The number and percentage of participants reporting any TEAE will be tabulated by system organ class and preferred term for each treatment (coded using Medical Dictionary for Regulatory Activities [MedDRA] version 24.1 or later). All TEAEs will be further classified by severity and relationship to treatment.

CONFIDENTIAL

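### The TEAE definition has no worsening clause: an AE that starts before insertion and intensifies on the ring falls outside the TEAE tables, and a worsened baseline symptom enters them only if the site records it as a new AE

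*Combined protocol and SAP*

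**What the plan says.** Section 7.7.1 gives the definition: "Treatment-emergent AEs (TEAEs) will be those with an onset after insertion of the first IVR through the follow-up telephone call". Section 8 uses the same test, saying that TEAEs "will be those with an onset after insertion of the first IVR through the follow-up telephone call". Neither section mentions a condition that was present earlier and becomes worse. The TEAE row of Table 1-1 adds only when collection starts.

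Section 9.4.1 lists "Incidence and severity of AEs" first among the primary endpoints. Section 9.6 then specifies the main tables for TEAEs: "The number and percentage of participants reporting any TEAE will be tabulated by system organ class and preferred term for each treatment", followed by "All TEAEs will be further classified by severity and relationship to treatment". Section 9.6 also promises a general descriptive summary of AEs.

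The underlying AE definition in Section 8 is broad. It takes in "any unfavorable and unintended sign, symptom, or disease temporally associated with the use of a study drug/product", whether or not it is thought to be related. Section 8.1 requires AEs to be entered on the AE page of the eCRF. AEs are monitored from consent (Section 7.7.1), and women using HRT may begin washout only after consent (Section 4.1).

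Exclusion 10 in Section 5.2 bars "Self-reported or observed vaginal irritation unrelated to VVA", so irritation that is part of VVA is not barred by that wording. "Vaginal and/or vulvar irritation/itching" is one of the symptoms rated at Cycle 1 Day 1 under Section 7.8.4.

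**The concern.** The expected local effects of a vaginal ring overlap with what postmenopausal women may already have. Itching can be a baseline VVA symptom, and vulvovaginal pruritus is among the most frequent TEAEs listed for the Phase 1 study in Section 2.3.1.2. If such a symptom is present before insertion and becomes worse on the ring, a definition that looks only at first onset does not clearly count it.

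The tables affected carry the first primary endpoint. Whether on-ring worsening appears in them could depend on how each of about two sites reads the AE definition. Any resulting error runs one way within an arm, towards fewer or milder local TEAEs. The effect on the contrast between the two doses cannot be signed, because omissions could occur in either arm.

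**Working it through.** The plan states no figure on this point, so the check is mainly textual, with simple arithmetic for scale.

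**Step 1. Apply the definition to three cases.**

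| Case | Onset relative to first insertion | In the Section 9.6 TEAE tables? |
|---|---|---|
| A. New symptom on the ring | After | Yes |
| B. AE that starts between consent and Day 1, then intensifies on the ring | Before | No, as written |
| C. VVA symptom present at baseline, not recorded as an AE, then worsens on the ring | Symptom before; aggravation after | Only if the site records the aggravation as a new AE |

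**Step 2. Can cases B and C occur?** For B, Section 4.1 requires at least 4 weeks of washout after transdermal products and at least 8 weeks after oral or intrauterine ones. For women still on HRT this follows consent, so there is a monitored period of weeks before insertion. For C, exclusion 10 leaves room for VVA-related irritation, and Table 7-2 rates irritation/itching from none to severe. The other entry criteria narrow C: a normal vagina on examination is required, and lesions, tenderness, visible infection and symptomatic bacterial vaginosis are barred. They do not rule it out.

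**Step 3. Does another section supply the missing rule?** Section 8.1 (recording fields), 8.2.2 (intensity) and 8.2.3 (relationship) are silent on worsening. Sections 7.7.2, 7.7.4 and 7.7.5 say when laboratory, vital-sign and physical-examination abnormalities become AEs; there is no equivalent for a symptom that intensifies. Footnote c to Table 1-1 uses the Cycle 1 Day 1 speculum examination to separate baseline abnormalities from ring-related AEs, but does not say what to do if a baseline finding worsens.

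**Step 4. Where else might worsening show?**
- The diary (Appendix C) has Yes/No items, so a woman with itching before and after insertion answers Yes both times.
- The usability questionnaire rates ring comfort on Day 1 of Cycles 2 and 3 and at EOS/ET.
- VVA symptoms are re-rated only at EOS/ET in Table 1-1, although Section 7.8.4 speaks of later visits in the plural. They feed an exploratory mean change, in which improvement can offset worsening.
- Speculum change is a primary endpoint but captures signs, not symptoms.

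None of these turns worsening into a TEAE.

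**Step 5. Scale.** Input: n = 10 per arm (Section 9.1).
- Preferred-term rate: shift per uncounted woman = 1/10 = 10 percentage points. For example, 1/10 = 10% (exact 95% CI 0.3% to 44.5%) would be reported as 0/10 = 0% (0% to 30.8%).
- Any-TEAE incidence: the shift is 10 points if she has no other TEAE and 0 otherwise. For example, 7/10 = 70% (34.8% to 93.3%) would become 6/10 = 60% (26.2% to 87.8%).
- Frequency: the documents give no rate of baseline symptoms that worsen. If a per-woman probability q of uncounted worsening is assumed, the chance of at least one such woman in an arm is 1 − (1 − q)^10. This gives 40% for q = 5%, 65% for 10%, 89% for 20% and 97% for 30%. These values of q are assumptions used to show a range; none is an estimate.

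**The case against.** The strongest reply is that the text already covers worsening. Ring-associated aggravation is itself an untoward, temporally associated occurrence. Section 8.1 makes recording of AEs mandatory, and the aggravation begins after insertion, so it meets the TEAE definition. For case C this is a reasonable reading. It is the reason not to infer that the plan excludes every worsened baseline symptom: the documents leave that open. But the reading has to be constructed, and no section states it. It does not help case B, where the AE already has an onset before insertion.

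A second reply is that the rule may sit elsewhere. Section 9 defers analyses to a separate SAP, and Section 13.1.1 refers to specific eCRF instructions. Neither was available, so the finding concerns the protocol text only. Even so, a SAP cannot tabulate an event that a site never recorded, so the recording instruction is needed at site level.

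A third reply concerns the Phase 1 link, and it stands in part. The Section 2.3.1.2 list covers terms above 10% in at least one dosage group, and oral treatment was one of the groups. A reader might infer that the rings produced the pruritus and burning; the list cannot be assigned to a ring arm. Burning is also not a Table 7-2 symptom, so only itching directly matches a baseline-rated item.

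Finally, this is a descriptive, open-label study of about 20 women with no AE hypothesis or decision threshold. That limits the consequences but does not remove the ambiguity in a primary-endpoint table.

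**Conclusion.** The point holds for the protocol text. Case B is outside the TEAE tables as written; case C depends on an interpretation that the protocol does not state. It is a gap worth closing, not a flaw that undermines the study.

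The size is 10 percentage points on a preferred-term rate per uncounted woman, and either 0 or 10 points on any-TEAE incidence. The number of women affected cannot be estimated.

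Two stronger readings of the size should be resisted. One is that every uncounted woman lowers any-TEAE incidence by 10 points; that is true only if she has no other TEAE. The other is that the Phase 1 product-related TEAE rates (70% for Dose 1, 58.3% for Dose 2) could serve as the chance that she has another TEAE and so bound the average shift. Those rates can include the same local terms that are in question, so they are not a floor for having a different event, and no average-shift bound is supported.

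The conclusion assumes that neither the SAP nor the eCRF instructions already contain a worsening rule.

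**What to change.** In Sections 7.7.1 and 8, define a TEAE as an AE with onset after first IVR insertion, or a condition or AE present before insertion that, in the investigator's judgement, increases in intensity afterwards. Keep the existing window through the follow-up call.

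In Section 8.1, instruct sites to record such worsening as an AE with the date of worsening, graded on the Section 8.2.2 intensity scale. The Cycle 1 Day 1 VVA ratings and speculum findings should serve as supporting reference only. State that a change in VVA rating is not by itself a TEAE: those ratings use a different scale and are scheduled only at Cycle 1 Day 1 and EOS/ET in Table 1-1, so they cannot trigger the classification automatically.

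Carry the same rule into the SAP, and into the eCRF instructions if it is not already there.

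The cost is one clause in two sections, one recording instruction and one SAP sentence. No visit or assessment is added. Reported TEAE rates may be slightly higher, and investigators will have to judge worsening between the two graded VVA assessments.

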7.7.2 Laboratory Tests

A certified laboratory will be utilized to process and provide results for the clinical laboratory tests listed in Table 7-1. The baseline laboratory test results for clinical assessment for a particular test will be defined as the last measurement prior to the first administration of study product.

Participants will fast for a minimum of 8 hours prior to clinical laboratory sample collection at screening. For subsequent clinical laboratory sample collections, participants will not be required to be fasted.

During screening, if a participant has an out-of-range value for a clinical laboratory parameter that the investigator believes is not clinically significant or the investigator does not believe is correct (e.g., laboratory or specimen processing error), but the investigator wants to confirm with a repeat laboratory test, a single repeat is allowed to confirm the initial result.

Additional safety laboratory tests may be conducted as needed by the investigator to evaluate participant safety.

CONFIDENTIAL

Table 7-1: Clinical Laboratory Tests

Hematology	Chemistry	Urine Dipstick
Hematocrit	Albumin	Specific gravity
Hemoglobin	Alkaline phosphatase	Ketones
Red blood cell count	Alanine aminotransferase	pH
White blood cell count	Aspartate aminotransferase	Protein
Neutrophils (absolute)	Gamma glutamyl transferase	Blood
Lymphocytes (absolute)	Direct bilirubin	Glucose
Monocytes (absolute)	Total bilirubin	Leukocyte esterase
Basophils (absolute)	Lactate dehydrogenase	Microscopic analysis (performed if blood, leukocytes, or protein are present)
Eosinophils (absolute)	Total protein	Nitrites
Platelet count (estimate not acceptable)	Blood urea nitrogen	
	Creatinine	
	Calcium	
	Phosphate	
	Sodium	
	Potassium	
	Bicarbonate	
	Chloride	
	Glucose ^a	
	Total cholesterol	
	Triglycerides ^a	

a. Fasting, at screening visit

For any laboratory test value outside the reference range that the investigator considers to be clinically significant during the on-study period (i.e., following dose administration), the investigator will:

- Repeat the test to verify the out-of-range value and clinical significance
- Follow the out-of-range value until the value returns to normal or baseline, or until the value is deemed stable and not clinically significant by the investigator
- Record as an AE any laboratory test value that is confirmed by repeat and which:
 - the investigator considers clinically significant
 - requires a participant to be discontinued from the study
 - requires a participant to receive treatment, or
 - requires a change or discontinuation of the study product (if applicable)

CONFIDENTIAL

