Endometrial biopsy ^d	X ^e															
Height (cm), weight (kg), and BMI ^f	X	X			X					X			X			
12-lead ECG	X															
Vital signs (BP and PR), RR, oral temperature	X	X		X	X		X	X	X	X		X	X			
Hematology and blood chemistry	X	X		X	X		X	X	X	X		X	X			
Urine dipstick	X	X			X					X			X			
FSH	X															

CONFIDENTIAL

Study Procedure	Screening	Cycle 1			Cycle 2					Cycle 3			EOS / ET		Follow-Up Phone Call
		Days -28 to -2	1	2, 3	8, 15, 22	1	2, 3	8	15	22	1	2, 3	8, 15, 22	29	
Serology tests ^g	X														
Drug and alcohol urine screen	X	X													
Training on use of IVR	X	X													
Randomization		X ^h													
Dispense IVR(s)		X			X					X					
Insert new IVR (after predose PK sample) ⁱ		X			X					X					
Remove used vaginal ring/return IVR(s)					X					X			X		
Confirm IVR placement		X ^j	X	X	X ^j	X	X	X	X	X ^j	X	X			
PK blood samples ^k	X	X ^l	X	X	X ^l	X	X	X	X	X ^l	X	X	X ^m	X ^m	
Usability and Tolerability questionnaire					X					X			X		
Vulvovaginal atrophy symptoms including most bothersome symptom		X											X		
MENQOL questionnaire		X											X		
Dispensing / Review of daily diary	X				X					X			X		
Adverse events, including serious adverse events	Adverse events and serious adverse events collected beginning at ICF signing and in an ongoing manner														
TEAEs	TEAEs collected beginning at IVR placement and in an ongoing manner as appropriate														
Prior/concomitant medications	X	Concomitant medications collected in ongoing manner, as appropriate													
Follow-up telephone call ^a															X

Abbreviations: AE = adverse event; BMI = body mass index; BP = blood pressure; ECG = electrocardiogram; EOS = end of study; ET = early termination; FSH = follicle-stimulating hormone; HCV = hepatitis C virus; HIV = human immunodeficiency virus; ICF = informed consent form; ID = identification;

CONFIDENTIAL

IVR = intravaginal ring; MENQOL = Menopause-specific Quality of Life; PK = pharmacokinetic; PR = pulse rate; RR = respiratory rate; SAE = serious adverse event; TEAE = treatment-emergent adverse events; temp = temperature.

- a. Participants undergoing washout of prior hormone replacement therapy will be required to sign the ICF before starting washout. Where washout of HRT will take approximately 8 weeks, screening procedures should not commence until 28 days prior to Cycle 1, Day 1.

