14. Participants with a history of any severe acute or chronic medical or psychiatric condition or laboratory abnormality that could increase the risk associated with trial participation or study treatment administration or could interfere with the interpretation of trial results and, in the judgment of the investigator, would make the participant inappropriate for entry into the trial. This includes but is not limited to the following:
 - a. Human immunodeficiency virus (HIV) infection (confirmed by medical history/serology testing),
 - b. Active chronic hepatitis B or hepatitis C infection including hepatitis B surface antigen and hepatitis C antibody positive participants with or without abnormal liver enzymes (confirmed by medical history/serology testing),
 - c. Concurrent neurodegenerative disease,
 - d. Cardiovascular: uncontrolled hypertension, unstable angina, myocardial infarction or symptomatic congestive heart failure within the past 6 months, serious uncontrolled cardiac arrhythmia, use of Class 1 antiarrhythmic medications, or history of venous thromboembolism or stroke,
 - e. Dementia or significantly altered mental status that would prohibit the understanding or rendering of informed consent and compliance with the requirements of the protocol,
 - f. Participants with known thrombophilias may not participate in this study because estrogen-based products are contraindicated for them,
 - g. Symptomatic bacterial vaginosis.
15. Fasting triglyceride of > 3.39 mmol/L and/or total cholesterol of > 7.77 mmol/L.
16. Aspartate aminotransferase or alanine aminotransferase > 1.5 times the upper limit of normal.
17. Fasting glucose > 6.94 mmol/L.
18. Evidence of current alcohol or drug abuse in the past 60 days including a positive result from the urine drugs of abuse or alcohol screen, or history of drug or alcohol dependence in the last 2 years, as assessed by principal investigator. Alcohol abuse is defined as greater than 14 standard units/week for females and drug abuse is defined as known psychiatric or substance abuse disorder that would interfere with participation with the requirements of this study, including current use of any illicit drugs. Use of medical cannabis is not exclusionary.
19. Participation in any other investigational drug or device trial in which administration of an investigational study drug/device occurred within 30 days or placement of a non-drug eluting medical device within 15 days prior to screening.

CONFIDENTIAL

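### Change from baseline in glucose and triglycerides is taken between samples whose fasting state is neither controlled nor stated to be recorded

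*Combined protocol and SAP*

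**What the plan says.** - **Fasting rule (Section 7.7.2).** "Participants will fast for a minimum of 8 hours prior to clinical laboratory sample collection at screening". After that, "For subsequent clinical laboratory sample collections, participants will not be required to be fasted". The footnote to Table 7-1, "a. Fasting, at screening visit", is attached to two analytes only, glucose and triglycerides.
- **Baseline (Section 7.7.2).** For each laboratory test, baseline is "defined as the last measurement prior to the first administration of study product".
- **Schedule (Table 1-1).** The row "Hematology and blood chemistry" is marked at screening, again on Cycle 1 Day 1, and at later visits through Cycle 3 Day 29.
- **Endpoint (Section 9.4.1).** "Changes from baseline in clinical laboratory findings" is listed among the primary endpoints, with no analyte set apart. Section 9.6 adds a qualitative analysis of laboratory abnormality and does not mention fasting.
- **Eligibility limits (Section 5.2).** Criterion 17 reads "Fasting glucose > 6.94 mmol/L", and criterion 15 sets a fasting triglyceride limit of 3.39 mmol/L. The opening of Section 5.2 also lets the investigator, in consultation with the medical monitor, discontinue participants "if they develop any of the exclusion criteria during the study".

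**The concern.** The protocol treats fasting as relevant to two analytes, and then applies it to the one sample that will usually not serve as baseline. A predose Day 1 draw becomes the reference for every change score, and neither it nor any follow-up draw has a fasting requirement or a stated fasting-status field. Differences between visits in when and what a woman ate then add to the variance of her change. With 10 women per arm there is little averaging to absorb it.

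There is also a second route. The protocol does not say that the Day 1 chemistry sample is drawn before insertion. PK sampling that day runs from 1 hour before insertion to 8 hours after, so both predose and postdose draws are possible. If the draw is postdose or missed, the baseline definition falls back to the fasted screening value. Change then compares a fasted sample with follow-up samples that may be fed.

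At stake is how clearly a metabolic shift over 12 weeks could be seen, or ruled out, for these two analytes.

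**Working it through.** **Plan's own figure.** There is none to reproduce. Section 9.1 sets 20 participants (10 per arm) by judgement, and no laboratory SD, effect size or error rate is given.

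**Step 1: count the draws (Table 1-1).** Screening 1; Cycle 1 Days 1, 8, 15, 22 = 4; Cycle 2 Days 1, 8, 15, 22 = 4; Cycle 3 Days 1, 8, 15, 22, 29 = 5. The total is 14. One has a required fast and 13 do not: Cycle 1 Day 1 plus 12 later draws. With 20 participants that is up to 12 × 20 = 240 post-baseline values for each of the two analytes.

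**Step 2: which value is baseline?**

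| Day 1 chemistry draw | Baseline sample | Follow-up | Consequence |
|---|---|---|---|
| Predose | Day 1, fasting not required | Fasting not required | Same rule on both sides: extra variance, no systematic shift expected |
| Postdose or missing | Screening, fasted | Fasting not required | Possible systematic shift as well as variance |

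In the second row, let *d* be the average difference between follow-up samples as taken and the same samples taken fasted. The documents give no value for *d*. If one woman in an arm of 10 falls back to screening, the arm's mean change shifts by about *d*/10. If the draw is routinely postdose, the shift is about *d*.

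**Step 3: illustration in mmol/L (triglycerides; both SDs are assumptions).** Let the within-woman SD be 0.25 when fasted, with an independent meal component of 0.3, 0.4 or 0.6 added to each sample. The half-width of a 95% interval for within-arm mean change at n = 10 is 2.262 × √2 × SD / √10 = 1.012 × SD.

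| Added SD | Total SD | Half-width | Ratio to fasted |
|---|---|---|---|
| none | 0.25 | 0.25 | 1.0 |
| 0.3 | √(0.25² + 0.3²) = 0.391 | 0.40 | 1.6 |
| 0.4 | √(0.25² + 0.4²) = 0.472 | 0.48 | 1.9 |
| 0.6 | √(0.25² + 0.6²) = 0.650 | 0.66 | 2.6 |

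**Step 4: the same idea without units.** Let *k* be meal-related variance as a multiple of the fasted change variance. The half-width in fasted-change SDs is (2.262/√10) × √(1 + *k*) = 0.715 × √(1 + *k*), and the equivalent sample size is 10/(1 + *k*).

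| *k* | Half-width (SD) | Equivalent n per arm |
|---|---|---|
| 0 | 0.72 | 10 |
| 0.25 | 0.80 | 8.0 |
| 0.5 | 0.88 | 6.7 |
| 1 | 1.01 | 5.0 |
| 2 | 1.24 | 3.3 |

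The assumed SDs in Step 3 correspond to *k* = 0.3²/0.25² = 1.44 up to 0.6²/0.25² = 5.76. Step 3 therefore sits at and beyond the upper end of this table. If most women happen to arrive fasted, or eat much the same before each visit, *k* is small and so is the loss.

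**The case against.** The strongest case on the other side is that non-fasting safety chemistry after a fasted screening is a deliberate, clearly stated choice. With a Day 1 baseline, the same rule governs both ends of the change. The visits are in the morning, which partly standardises time of day. Only two of the 20 chemistry tests in Table 7-1 are affected, the laboratory endpoint is descriptive, and no confidence interval for laboratory change is planned. All of that stands. It limits the weight of the point but does not remove the avoidable variance.

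Three stronger readings are tempting, and the documents do not support them:

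- **That the Day 1 baseline is unfasted.** The text says fasting is not required. The state is unknown, and some women may arrive fasted.
- **That the change is biased by design.** A shift is expected only on the fallback to screening. Otherwise the effect is noise.
- **That on-study values are judged against fasting limits and so generate false adverse events.** Criteria 15 and 17 are worded as fasting limits and can be checked on the fasted screening sample. They reach later samples only through the discretionary on-study clause in Section 5.2 or the Day 1 eligibility assessment in Table 1-1. Section 7.7.2 allows additional tests as needed, which leaves room for a fasted retest. An out-of-range value is recorded as an adverse event only after a judgement of clinical significance and a confirming repeat. Whether the reference ranges are fasting or non-fasting is not stated.

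What remains of the last reading is a gap: no scheduled on-study sample has to meet the condition in those criteria, and the text does not say how the two relate.

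Section 9 leaves analysis detail to a separate statistical analysis plan. Such a plan could define the tables, but it could not recover fasting status that was never collected.

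**Conclusion.** The point holds as a modest design improvement. The only sample with a required fast is displaced as baseline whenever the Day 1 draw is predose. The fasting state of the Day 1 baseline and of 12 later draws is uncontrolled and not stated to be recorded. For glucose and triglycerides this adds meal-related variance to part of a primary safety endpoint, and a missing or postdose Day 1 sample can add a systematic shift.

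The size for this trial cannot be computed from the documents. The triglyceride half-widths rest wholly on assumed SDs and on independent meal effects in every sample. They show how 10 women per arm would respond to such noise, and they are not an estimate. No figure is offered for glucose. Nothing here calls the safety conclusions as a whole into question.

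**What to change.** 1. Require the same 8-hour fast before chemistry on Cycle 1 Day 1 and Cycle 3 Day 29, both already morning visits, and state that the Day 1 draw is predose.
2. Record fasting status at every chemistry draw, including early termination.
3. Use the fasted Day 1 to Day 29 pair for the 12-week change in glucose and triglycerides.
4. Keep reporting all other glucose and triglyceride values, flagged by fasting status. Restricting the tables to fasted samples could drop the values from up to 11 of the 12 post-baseline draws, which a 12-week safety study should not give up.
5. State which type of reference range applies to these two analytes on study, and reconcile Sections 5.2 and 7.7.2 on how the fasting-worded criteria relate to on-study samples. No clinical rule is proposed here.

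The cost is an overnight fast before two existing visits, which is a slight burden on participants, and one eCRF field.
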